3.3.7. Definitions and Terminology

Age

The age of a subject is defined as the number of whole years between the subject's birth date and the date of screening. If a subject is anticipated to turn 12 between screening and randomization, he/she will be randomized into the adolescent group but will use the Wong Baker and the mBSFS. A subject who turns 12 during the treatment period or post-treatment follow-up period will remain in 6 to 11 years age group and will use the Wong Baker and the mBSFS. The questionnaires will be provided based on the age at Screening.

All subjects in 6 to 11 years old age group are expected to get the parental oversight on eDiary records. All subjects in 12 to <18 years old age group can complete eDiary by themselves but should be discussed with parent.

Baseline Value

For purposes of safety analysis, the baseline value is defined as the last non-missing value obtained prior to the randomization.

For purposes of efficacy analysis, the baseline values will be derived from data collected in the 2-week electronic diary assessment at the end of the Screening Period (baseline). The last 14 days of diary entries prior to Day 1 will be the default standard for derivation of these values.

The baseline BM (SBM, CSBM) weekly rate will be the weekly average number of BMs (SBMs, CSBMs) recorded during the 2-week baseline assessment period; similarly, for frequency of abdominal pain and abdominal discomfort, frequency of fecal incontinence, frequency of defecation pain, and frequency of large diameter stools. Baseline stool consistency, severity of abdominal pain, abdominal discomfort, and severity of defecation pain will be calculated as follows: for each week of the baseline assessment, the weekly average is the sum of the non-missing scores recorded during the week divided by the total number of non-missing scores recorded during that week; the baseline is then equal to the average of the 2 weekly average scores defined as sum of the 2 weekly average scores divided by 2.

Day 1 (Baseline)

Day 1 is the earliest day that study drug is initiated.

Study Day

Study Day is defined relative to Baseline (Day 1). Thus, the study day of an event is calculated as:

Study Day = Event Start Date – Baseline Date + 1, for dates on or after Day 1;

Study Day = Event Start Date – Baseline Date, for dates before Day 1.

Study Visit

Study Visit is the nominal visit as recorded on the CRF.

Change from Baseline

Change from baseline for a given endpoint is defined as the Study Visit value minus the Baseline Value.

Last Dose of Plecanatide

Last Dose of Plecanatide is defined as the last date that the subject received Plecanatide as determined by last date of dosing as recorded on the Study Drug Administration CRF.

Duration of Plecanatide

Duration of Plecanatide is defined as the number of days from Day 1 to the date of Last Dose of Plecanatide.

Duration on Study

Duration on study is defined as the number of days from the date of screening to the date of last follow-up visit.

Dosing Compliance

Dosing compliance will be defined by the dosing compliance ratio: the number of doses actually taken by the subject divided by the number of doses that were expected to be taken during the same period multiplied by 100.

Treatment Compliance

Treatment compliance is defined as taking equal to or greater than 80% of the drug dosage prescribed. Otherwise, the subject will be considered noncompliant with study treatment.

Rescue Medication

Dulcolax® will be provided as a rescue laxative that can be used if a subject has not had a bowel movement for at least 72 hours. Subjects will be advised that it is preferred that they do NOT take rescue medication for the period from 24 hours before to 72 hours after Day 1 of dosing.

Adverse Event

An adverse event (AE) is any untoward medical occurrence associated with the use of a drug in humans, whether or not considered to be drug related. An AE can therefore be any unfavorable and unintended sign (including abnormal laboratory finding), symptom, or disease temporally associated with the use of an investigational product or study procedure whether or not considered related to the product or procedure.

Specific gastrointestinal symptoms related to IBS-C recorded daily in the electronic Diary will be summarized separately and generally not also recorded as Adverse events.

Treatment-emergent Adverse Event

A treatment emergent adverse event (TEAE) is defined as an AE that begins or worsens in frequency and/or severity after at least one dose of study drug has been administered. Additionally, it is assumed that an Adverse Event which was reported to have started on Day 1 without an associated onset time occurred after the initiation of study drug is treatment-emergent.

Treatment-emergent Laboratory Toxicities

A Treatment-emergent Laboratory Toxicity is defined as any post-baseline laboratory assessment occurring up to and including 14 days post treatment discontinuation representing an increase of 1 grade or more from the baseline toxicity value. If the baseline value is missing, any graded toxicity (grade 1 or higher) that occurs following initiation of treatment is considered treatment-emergent.

Spontaneous bowel movement (SBM)

A bowel movement that occurs in the absence of laxative use within the preceding 24 hours.

Complete spontaneous bowel movement (CSBM)

A spontaneous bowel movement with the sense of complete evacuation.

Weekly BM (SBM, CSBM) Rate

Weekly BM (SBM, CSBM) rate is the sum of the BMs (SBMs, CSBMs) recorded for the days in the week for which a BM (SBM, CSBM) response is recorded in the daily diary.

In any analysis of the frequency of abdominal pain, frequency of abdominal discomfort, frequency of fecal incontinence, the frequency of defecation pain, and the frequency of large diameter stools will follow the same methodology as described above for the determination and analysis of the weekly BM rate.

Weekly Average Abdominal Pain Score

Weekly average IBS-related daily abdominal pain score is the average of the non-missing, abdominal pain scores recorded in that week, i.e., the weekly average is the sum of the abdominal pain scores recorded in the diary in the given week, divided by the number of pain scores recorded in the week.

Weekly Average Defecation Pain Score

Weekly average item score is the sum of the non-missing defecation pain scores recorded during the week, divided by the total number of non-missing defecation pain scores recorded.

Weekly Average Stool Consistency

Stool consistency is the sum of the non-missing stool consistency scores recorded during the week, divided by the total number of non-missing stool consistency scores recorded. Note stool consistency cannot be assessed if the subject does not have at least one SBM during the week in question (i.e., stool consistency is based on SBMs only).

Concomitant Medications

Concomitant medications are those medications taken on or after the initiation of study drug. This definition includes medications started prior to the initiation of study drug but continuing concomitantly with study drug.

Prior Medications

Prior medications are those medications taken and ended prior to the initiation of study drug.

Post Medications

Post medications are those medications started after the last dose of study drug.

3.4. TIMING OF ANALYSES

The final data analysis will be performed after all subjects have either completed or have been discontinued from the study. The study will be unblinded after subject membership in each of the various analysis populations has been determined at a blinded data review meeting and upon confirmation of database lock.

No interim analyses are planned.

4. ANALYSIS POPULATIONS

The populations for analysis will include full analysis set (FAS) population, per protocol (PP) population, safety population, and intensive PK population.

4.1. FULL ANALYSIS SET (FAS)

All randomized and treated subjects who had the baseline assessment and at least one post randomization assessment of the primary efficacy measure of weekly SBM frequency. The FAS is the main population for assessments of efficacy. Subjects will be analyzed according to the treatment assigned

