On 19 January 2017 and 24 January 2018, the FDA approved plecanatide (Trulance[®], 3 mg dosage strength) for the treatment of CIC and IBS-C, respectively in adults. Approval was based on efficacy and safety data from 3182 adult patients (1733 CIC and 1449 IBS-C) who were enrolled in four double-blind placebo-controlled clinical trials and received placebo or 3 mg Trulance once daily for 12 weeks. Additional safety data are available from a total of 9615 patients enrolled in these four studies and two longer-term chronic therapy studies of up to 72 weeks. The most common adverse reaction (reported in at least 2% of Trulance treated patients and at an incidence greater than placebo) was diarrhea 5.0% and 4.3% in the Trulance group (CIC and IBS-C, respectively) and 1% in the placebo group for each indication. The majority of reported cases of diarrhea occurred within 4 weeks of treatment initiation. In the CIC population, severe diarrhea

was reported in 0.6% of Trulance-treated patients compared to 0.3% of placebo-treated patients and was reported to occur within the first 3 days of treatment. In the IBS-C population, severe diarrhea was reported in 1.0% of Trulance treated patients compared to 0.1% of placebo treated patients and occurred within the first day of treatment.

Discontinuations due to adverse reactions occurred in 4.0% and 2.5% of Trulance-treated patients and 2.0% and 0.4% of placebo-treated patients; the most common adverse reaction leading to discontinuation was diarrhea in 2.0% and 1.2% of Trulance treated patients and 0.5% and 0% of placebo treated (CIC and IBS-C, respectively).

A description of the clinical trials, safety, and efficacy information can also be found in the Investigator's Brochure.

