8.3 ANALYSIS POPULATIONS

The following populations will be assessed:

Safety Population (SP):	All randomized patients who receive at least one dose of the study drug. Patients will be analyzed according to the treatment received. All safety analyses will be based on the Safety Population.
Full Analysis Set (FAS):	All randomized and treated patients who had the baseline assessment and at least one post randomization assessment of the primary efficacy measure of weekly SBM frequency. The FAS is the main population for assessments of efficacy.
Per Protocol (PP) Population:	All patients in the FAS population who complete the 4-week Treatment Period or discontinue from study treatment due to adverse event(s) or lack of efficacy, with the exception of major protocol violators. Criteria to identify

the PP population will be detailed in the SAP. Decisions regarding exclusion from the PP Population will be made prior to unblinding the database.

Efficacy analyses will be based on the FAS Population. Efficacy analyses will be repeated for the PP Population to assess the sensitivity of the analyses to the choice of analysis set.

Deviations from the study protocol, including violations of inclusion/exclusion criteria, will be assessed as “minor” or “major.”. Major deviations from the protocol will lead to the exclusion of a patient from the PP Population and will be determined prior to unblinding the study database. Missed telephone contact (TC) visits will not be considered deviations from the study protocol.

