8.4.1 Missing Data Conventions

Missing values of safety parameters will not be imputed.

The weekly BM (SBM, CSBM) rate is the sum of the BMs (SBMs, CSBMs) recorded for the days in the week for which a BM response is recorded in the daily diary. Note that this is equivalent to a “worst case” analysis in that the BM (SBM, CSBM) rate for the week is the sum of the BMs (SBMs, CSBMs) recorded for the days in the week for which BMs were reported, plus 0 BMs (SBMs, CSBMs) for each day in the week for which the BM response is missing. In any week in which no BM response is recorded, the weekly BM (SBM, CSBM) rate will be set to 0 in any summary or linear mixed-effects model analysis involving

the weekly BM (SBM, CSBM) rate. In particular, for a randomized patient who withdraws from study participation prior to the end of the study, the patient is considered to have a weekly BM (SBM, CSBM) rate equal to 0 for any weeks remaining in the planned duration of the study for which the patient has no BM responses recorded.

The weekly average IBS-related daily abdominal pain score is the average of the non-missing, abdominal pain scores recorded in that week, i.e., the weekly average is the sum of the abdominal pain scores recorded in the diary in the given week, divided by the number of pain scores recorded in the week. In any week in which a patient has no diary days for which an abdominal pain score is recorded, the weekly average abdominal pain score will be set to missing. In any linear mixed-effects model analysis involving the weekly average abdominal pain score, if the average score is set to missing in a given week, it will be left as missing in the linear model. In particular, for a randomized patient who withdraws from study participation prior to the end of the study, the weekly average abdominal pain score will be set to missing for any weeks remaining in the planned duration of the study for which the patient has no abdominal pain data.

In any analysis of the frequency of fecal incontinence, the frequency of defecation pain, and the frequency of large diameter stools will follow the same methodology as described above for the determination and analysis of the weekly BM rate.

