3.3.4. Missing Data

Missing values of safety parameters will not be imputed.

For each day in the week for which the Bowel Movement (BM) (includes Spontaneous Bowel Movement [SBM] and Complete Spontaneous Bowel Movement [CSBM]) response is missing, 0 BMs (SBMs, CSBMs) will be used, and any week in which no BM response is recorded, the weekly BM (SBM, CSBM) rate will be set to 0. In particular, for a randomized subject who withdraws from study participation prior to the end of the study, the subject is considered to have a weekly BM (SBM, CSBM) rate equal to 0 for any weeks remaining in the planned duration of the study for which the subject has no BM responses recorded.

In any analysis of the frequency of abdominal pain (discomfort), use of rescue medication, the frequency of fecal incontinence, the frequency of defecation pain, the frequency of large diameter stools, missing values will be imputed to zero.

In any analysis involving the severity of abdominal pain and discomfort, the weekly average IBS-related daily abdominal pain (discomfort) score is the average of the non-missing, abdominal pain (discomfort) scores recorded in that week, i.e., the weekly average is the sum of the abdominal pain (discomfort)

scores recorded in the diary in the given week, divided by the number of pain (discomfort) scores recorded in the week. In any week in which a subject has no diary days for which an abdominal pain (discomfort) score is recorded, the weekly average abdominal pain (discomfort) score will be set to missing. In particular, for a randomized subject who withdraws from study participation prior to the end of the study, the weekly average abdominal pain (discomfort) score will be set to missing for any weeks remaining in the planned duration of the study for which the subject has no abdominal pain (discomfort) data.

In any analysis involving the severity of defecation pain, the weekly averages are the sum of the non-missing severity of defecation pain scores recorded during the week, divided by the total number of non-missing severity of defecation pain scores recorded. In any week in which a subject has no non-missing severity of defecation pain scores recorded, the weekly average score will be set to missing in any summary or linear mixed-effects model analysis involving the weekly average severity of defecation pain score.

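### A dosed patient with no post-randomization diary record drops out of the FAS, although the plan's own missing-data rule would score that patient 0 SBMs in every week

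*Combined protocol and SAP*

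**What the plan says.** SAP 4.1 limits the FAS to patients who were randomized, took study drug, have a baseline, and also have "at least one post randomization assessment of the primary efficacy measure of weekly SBM frequency"; they are analysed by assigned treatment. Protocol 8.3 uses the same entry condition and adds: "The FAS is the main population for assessments of efficacy".

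The missing-data rule points the other way. Protocol 8.4.1: "In any week in which no BM response is recorded, the weekly BM (SBM, CSBM) rate will be set to 0". SAP 3.3.4 repeats this and, for a randomized subject who withdraws, adds that "the subject is considered to have a weekly BM (SBM, CSBM) rate equal to 0 for any weeks remaining in the planned duration" for which nothing was recorded. Protocol 8.4.1 describes the approach as a worst-case analysis.

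SAP 3.3.7 derives the weekly figure without a minimum number of diary days: "Weekly BM (SBM, CSBM) rate is the sum of the BMs (SBMs, CSBMs) recorded for the days in the week" that have a response. SAP 3.3.6 puts Day 1 in Week 1.

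The only planned repeat of the primary analysis is on the PP population (protocol 8.3, SAP 5.2.2), which is a subset of the FAS. The Safety Population (SAP 4.3) keeps every dosed patient, but only for safety.

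**The concern.** The two rules disagree about one kind of patient: dosed at Visit 2, then no diary record at all. The missing-data rule is written for any randomized patient who withdraws, and it would give this patient four weeks of 0. The FAS condition removes the patient before that rule can act. A patient who records one day and then stops is kept and scored 0 for the remaining weeks.

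The exclusion depends on something that happens after randomization and that treatment can influence. In the adult IBS-C data in protocol 2.1.5, 2.5% on drug and 0.4% on placebo stopped for adverse reactions, and 1.2% v 0% stopped for diarrhea. Protocol 6.3.1 says that pediatric patients may be at increased risk of diarrhea. If patients without a record are more common on drug, leaving them out favours plecanatide relative to the plan's own rule. The PP repeat could not show this, because they are already gone.

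**Working it through.** **Which patients are affected**

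| Patient | FAS rule | Missing-data rule |
|---|---|---|
| Logs at least one stool on Day 1, then stops | Has a Week 1 value; stays in | 0 for Weeks 2–4 |
| Dosed, records nothing after randomization; imputed 0 is not an assessment | Excluded | 0 for Weeks 1–4 |
| Same patient; imputed 0 is an assessment | Included; the condition excludes nobody on post-baseline grounds | 0 for Weeks 1–4 |

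The first row follows from four provisions: Day 1 is in Week 1 (SAP 3.3.6), bowel movements are logged in real time (protocol 4.2.1), any movement without a laxative in the previous 24 hours is an SBM, loose or not (SAP 3.3.7), and no minimum number of diary days is set.

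**The plan's power figure**

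Inputs (SAP 3.1): 102 v 34 patients, difference 1.5, SDs 3.5 and 2.3. I use two-sided alpha 0.05 (SAP 5); the 0.05% in the power text does not reproduce the stated figure.

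- Standard error = √(3.5²/102 + 2.3²/34) = 0.525.
- Power = Φ(1.5/0.525 − 1.96) = 0.815, which matches the stated 81.5%. A Welch t test gives 80.7%.
- At the planned Group B size, 90 v 30, the Welch figure is 75.5%.

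**How many patients**

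The documents give no rate for a missing diary. As upper limits, suppose adult IBS-C rates (protocol 2.1.5) carry over and every such patient records nothing. Table 3 gives 5 × 30 = 150 plecanatide and 2 × 30 = 60 placebo patients.

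| Adult event | Rate on drug | Expected of 150 |
|---|---|---|
| Severe diarrhea, first day | 1.0% | 1.5 |
| Stopped for diarrhea | 1.2% | 1.8 |
| Stopped for any adverse reaction | 2.5% | 3.75 |

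On placebo, 0.4% of 60 is 0.24. At 1.0%, the chance of at least one event among 150 is 1 − 0.99¹⁵⁰ = 78%. Protocol 6.3.1 gives 0.7% for severe diarrhea in adult IBS-C, where protocol 2.1.5 gives 1.0%. The two must be reconciled; at 0.7% the expected number is 1.05.

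**Effect on the estimate**

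Let f be the fraction with no record, b the baseline and m the mean change in the other plecanatide patients. Scoring these patients 0 gives each a change of −b, so the plecanatide mean falls by f × (m + b). Assumptions not in the documents: b = 1–4 SBMs per week, m = 1.5–3.5, so m + b runs from 2.5 to 7.5.

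- f = 1.0%: 0.025 to 0.075.
- f = 2.5%: 0.0625 to 0.1875. If 0.4% of placebo patients are also scored 0, with placebo change m − 1.5, the placebo mean falls by 0.004 × 1 = 0.004 to 0.004 × 6 = 0.024. The net fall in the difference is then 0.06 to 0.16.
- Equal fractions in both arms: the difference falls only by f × 1.5.
- One patient in a 30-patient dose arm: 2.5/30 to 7.5/30, or 0.08 to 0.25.

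With these patients included at 90 v 30, the plecanatide SD widened for them and no placebo patients affected, Welch power is 70–74% at 1.0% and 62–72% at 2.5%. The comparator must drop the excluded patients too: at 2.5% that leaves 87.75 v 30 and 75.0%.

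**The case against.** A reader might infer that immediate stoppers as a class, including children with first-day diarrhea, vanish from the primary analysis. The documents do not support that. Protocol 2.1.5 reports severe diarrhea in 1.0% on drug "compared to 0.1% of placebo treated patients and occurred within the first day of treatment", but those patients were having bowel movements, and one logged stool keeps a patient in the FAS. The figure is not evidence of empty diaries.

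A reader might also try a larger fraction, such as 5% on drug, and conclude that the effect is materially inflated. That is twice the adult IBS-C rate of stopping for any adverse reaction, and the adult rate covers stopping at any time in 12-week trials.

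Three further objections have force. The exclusion is a reading: the documents never say that an imputed 0 is not an assessment. The zero rule is itself a worst case, so the shift measures sensitivity to that rule and not error against a true effect. And the trial is described as exploratory, population membership is fixed at a blinded review, and Safety and FAS sample sizes will appear in the table headers, so the count by arm could largely be recovered.

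These limit the size and severity but do not remove the conflict. Either the condition excludes nobody on post-baseline grounds and serves no purpose, or it exempts the patients with least data from a rule meant to be conservative. Blinded review prevents deliberate selection; it does not prevent imbalance from unequal stopping.

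**Conclusion.** The conflict is in the text and holds for dosed patients with no post-randomization diary record, and for no one else. With adult IBS-C rates as upper limits and the assumed baseline and change, the shift is about 0.03–0.08 SBM per week at 1.0% and at most about 0.19 at 2.5%, against a planned difference of 1.5. The direction favours plecanatide only if such patients are more common on drug, which the adult stopping rates make plausible but do not show. The limits cover adverse-reaction stopping only; they would not hold if children stop more often than adults, and they do not cover diaries missing for other reasons. The likely effect on a pooled comparison is small, though a single patient can be visible in a 30-patient dose arm. Severity is minor.

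**What to change.** In SAP 4.1 and protocol 8.3, define the FAS as all randomized patients who took at least one dose, analysed as assigned, and delete the condition on a post-randomization assessment. Baseline data are not an obstacle, because diary eligibility before randomization already requires them (protocol 3.2 and 5.2.2). Apply the existing missing-data rule to patients with no diary record, and report their number by arm.

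If the condition is kept, state whether an imputed 0 counts as an assessment, and add a sensitivity analysis in all randomized and treated patients.

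The cost is one sentence in each document and one reported count. The primary model is unchanged. The downside is a possibly slightly less favourable estimate if these patients are concentrated on active drug.
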